In IVF cycles, basal serum AMH level was significantly correlated with AFC, the number of follicles obtained after stimulation and the number of retrieved oocytes, and has been found useful in prediction of suboptimal and excessive ovarian responses upon ovarian stimulation (Ficicioglu et al, 2006; Lekamge et al, 2007; Kwee et al, 2008; Broer et al, 2009; Ledger, 2010; Broer et al, 2011). It has been suggested that measurement of serum AMH can be used for patient-tailored individualization of the dosage of gonadotrophin used in ovarian stimulation during IVF treatment (Olivennes et al, 2009; Nelson et al, 2009; Yates et al, 2011). Compared to AFC, AMH has the advantage of having less intra- and inter-cycle variation (van Disseldorp et al, 2010) and is not operator-dependent, despite its additional cost. However, there is yet no prospective randomized trial to compare the performance of AFC and AMH in this regard.

Therefore, we propose this randomized trial to evaluate the role of baseline serum AMH and AFC for determination of gonadotrophin dosing in in-vitro fertilization treatment.

3. Objectives:

This is a prospective randomized trial to compare the use of AFC and serum AMH as the basis for gonadotrophin dosing in in-vitro fertilization treatment.

The hypothesis is that the use of serum AMH as the criterion for determination of gonadotrophin dosing in IVF treatment results in more optimal ovarian response than AFC.

4. Study design:

Patients undergoing the first-time IVF treatment cycle using either conventional insemination technique or intracytoplasmic sperm injection at Queen Mary Hospital will be invited to participate in this study. Participating subjects will be randomized into either (i) AFC or (ii) AMH group, where the gonadotrophin dosing will be determined based on the baseline AFC and serum AMH respectively as assessed one month before the IVF treatment.

Randomisation will be performed according to a computer-generated list which will be read by an independent research nurse. That research nurse will assign the initial gonadotrophin dose according to the study protocol. The clinician and patient will both be blinded to the randomization throughout the course of treatment. The proportion of subjects having appropriate ovarian response, defined as the number of oocytes retrieved being 6 to 14 inclusive (Broer et al, 2010), will be compared between the two arms.

5. Subject selection and exclusion

5.1 Inclusion criteria:

- Subjects undergoing the first IVF cycle during the study period.

5.2 Exclusion criteria:

- Body mass index ≥ 30 kg/m²
- Subjects in repeated IVF cycles
- Subjects undergoing IVF treatment using donor oocytes
- Subjects undergoing pre-implantation genetic diagnosis

6. Treatment of subjects

Subjects will attend the Assisted Reproduction Clinic on day 2-5 of the menstrual cycle preceding their scheduled IVF treatment. They will undergo transvaginal ultrasound examination to determine the AFC and assess for other pelvic abnormalities as what would be routinely done before IVF according to our usual protocol. **Blood (10 c.c.)** will also be taken for measurement of reproductive hormones including FSH, LH, E2 and AMH. The subjects will be asked for separate consent to archive the residual serum samples for future studies on reproductive endocrinology as appropriate (such future studies will be subject to approval by the HKU/HA HKWC IRB).

Subjects will be interviewed by a dedicated research nurse to explain on this study. Those who give written informed consent will be randomized into either the AMH or AFC groups according to a computer-generated randomization list.

(All participants will be blinded to AFC during ultrasound examination. A research nurse will keep the ultrasound sheets of all patients separately, which will be filed back to the patients' medical record upon completion of the ovarian stimulation.)

In their IVF treatment cycle, the ovarian stimulation regimen will be determined according to the randomization result as per the following table:

Gonadotrophin (FSH or HMG) regimen	AMH Group	AFC Group
300 IU daily	AMH ≤ 1.0 ng/ml	AFC ≤ 5
225 IU daily	AMH >1.0 and ≤ 3.3 ng/ml	AFC >5 and ≤ 15
150 IU daily	AMH >3.3 ng/ml	AFC >15

The AMH cut-off values are based on review of 214 patients previously treated in our centre who had AMH and AFC determined before ovarian stimulation. By regression

analysis, an AMH value of 1.0 ng/ml and 3.3 ng/ml corresponded to AFC of 5 and 15 respectively. Both linear and quadratic regression models gave roughly the same results.

The dose will be charted by the research nurse, and both the clinician and the patient will be blinded to the assigned group.

All subjects will be assessed by transvaginal ultrasound scan on the 7th day of ovarian stimulation, with the dose of gonadotrophin adjusted according to the ovarian response as detailed in the following table:

Response category	Criteria based on the number of follicles >10 mm (F10)	Action on gonadotrophin dose
Under-response	F10 ≤5	Step-up the dose: 150 → 225 IU daily, or 225 → 300 IU daily
Normal response	F10 >5 and ≤15	Keep at same dose
Excessive response	F10 >15	Step-down the dose: 225 → 150 IU daily 150 → 112.5 IU daily

The dose adjustment will be made for **once only** throughout the treatment cycle.

All subjects will be treated on a GnRH antagonist protocol for pituitary down-regulation. They will receive **cetorelix or ganirelix** 250 microgram subcutaneous injection starting from the 6th day of ovarian stimulation until the day of hCG trigger, according to our current clinic protocol.

Human chorionic gonadotrophin (hCG) will be administered for ovulatory trigger when the leading follicle reaches 18 mm, with preferably two or more other follicles reaching 16 mm in mean diameter. Oocyte retrieval will be carried out 34-36 hours post-hCG, where all follicles >10 mm will be aspirated.

All subjects will proceed to hCG trigger and oocyte retrieval except for those with zero follicle developing to beyond 10 mm after 12 days of stimulation, or when these are contraindicated for other medical reasons. Any events of ovarian hyperstimulation syndrome (OHSS) or anticipated risk of OHSS will be managed according to current practice.

7. Study outcomes

Primary outcome:

- Percentage of subjects having appropriate ovarian response (defined as number of oocytes retrieved being between 6 and 14).

Secondary outcome:

- Percentage of subjects requiring step-up or step-down of gonadotrophin dose upon first ultrasound tracking.

Hormone assay:

AMH concentration will be determined with ELISA using a commercial automated method (Access AMH Assay, Beckman-Coulter, Texas, USA), which has a limit of detection of 0.02 ng/ml.

8. Statistics

8.1 Statistical tests:

The percentage of subjects having appropriate ovarian response, defined as number of oocytes retrieved between 6 and 14 (Broer et al, 2010), as well as the percentage requiring step-up and step-down of gonadotrophin dose, will be compared between the AMH and AFC groups using χ^2 test or Fisher's Exact test as appropriate. Statistical analyses will be performed using the SPSS software.

8.2 Sample size estimation:

According to review of our Centre's data (unpublished), 50% of our patients have appropriate ovarian response when using AFC to determine gonadotrophin dosing as in current practice. Assuming that an increase to 70% of appropriate response in the AMH group will be clinically significant, we require a minimum of 93 subjects to demonstrate a significant difference between the AMH and AFC groups with 80% power and type I error of 0.05. To allow for drop-outs, a total of 200 subjects (i.e. 100 per group) will be recruited.

9. Assessment of safety

There is no safety concern as the study does not involve any extra medical intervention to the patients concerned. It only involves the comparison of two assessment tools for determination of gonadotrophin dosing. The use of AFC for this purpose is the current practice in our Centre, whereas the use of AMH for this purpose is well supported in recent literature.

10. Direct access to source data / documents:

Trial-related monitoring, audits and regulatory inspections are allowed.

11. Quality control and quality assurance

This shall follow the general quality control policy established for our clinic as well as for our hormone assay laboratory.

12. Ethics:

Ethics approval will be applied for before commencement of study.

13. Data Handling and record keeping

All data will be stored and analysed using SPSS. All the investigators will be responsible for data management including data coding, monitoring and verification.

14. Financing and insurance

The study will be funded by the Department of Obstetrics and Gynaecology, University of Hong Kong.

15. Publication policy

The findings of this study will be submitted for consideration for publication in peer-reviewed scientific journal.

16. Supplements

Nil

References:

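### The AMH and AFC rules will give a substantial but unreported share of women the same starting dose; the 20-point target is not checked against that share, and the analysis leaves precision unused.

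*Combined protocol and SAP*

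**What the plan says.** Section 6 gives both arms the same three starting doses (300, 225 and 150 IU daily). In the AFC group the dose steps at counts of 5 and 15. In the AMH group it steps at levels taken from a regression in 214 earlier patients of the centre, in whom "an AMH value of 1.0 ng/ml and 3.3 ng/ml corresponded to AFC of 5 and 15 respectively". The background text before section 3 notes that "basal serum AMH level was significantly correlated with AFC". Section 6 does not report how often the two rules gave those 214 patients the same dose.

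Every woman has both markers measured in the cycle before treatment: AFC by ultrasound, and blood that "will also be taken for measurement of reproductive hormones including FSH, LH, E2 and AMH". The day-7 adjustment rule is the same in both arms, and "both the clinician and the patient will be blinded to the assigned group".

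Section 8.2 starts from the centre's experience that "50% of our patients have appropriate ovarian response when using AFC to determine gonadotrophin dosing" and continues: "Assuming that an increase to 70% of appropriate response in the AMH group will be clinically significant, we require a minimum of 93 subjects". It recruits 100 per group. Section 8.1 says that the percentages "will be compared between the AMH and AFC groups using" a chi-square or Fisher's exact test. It plans no analysis by whether a woman's two dose bands agree.

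**The concern.** A woman is concordant if both rules put her in the same dose band, and discordant if they do not. A concordant woman gets the same starting dose, the same day-7 rule and the same blinded care whichever arm she is in. Only discordant women can produce a difference between arms. Because the cut-offs were matched and the markers are correlated, the concordant share should be substantial.

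Two things follow. First, whether 20 points over a whole arm is plausible depends on d, and section 8.2 does not consider d. If d is modest, a real benefit in the women whose dose changes appears as a small overall difference that 100 per arm will probably miss. A reader could then take the null result as evidence that AMH doses no better than AFC. Second, concordant women add random noise but no signal to the whole-arm comparison. Discordance is known at baseline for every woman, so the plan could remove that noise at no cost in patients.

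**Working it through.** **1. The plan's own figure.** Inputs from section 8.2: 50% versus 70%, 80% power, alpha 0.05 (taken as two-sided).

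n per group = [1.96 × √(2 × 0.6 × 0.4) + 0.842 × √(0.5 × 0.5 + 0.7 × 0.3)]² / 0.20² = (1.358 + 0.571)² / 0.04 = 93.

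The stated 93 is right as a per-group number. Power is 80.0% at 93 per arm and about 83% at 100.

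**2. Dilution.** Difference over all women = d × (difference in discordant women) + (1 − d) × 0.

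**3. Range for d.** This is an assumption, because the documents give neither a correlation coefficient nor the shares in each band. It comes from a bivariate normal model with equal band shares under both rules and five illustrative splits (10/65/25, 20/55/25, 15/70/15, 10/50/40 and 30/50/20):
- correlation 0.6 to 0.9: d about 17% to 44% (16% to 48% if regression-mapped cut-offs are also allowed);
- correlation 0.3: d up to about 55%;
- no correlation: d = 1 − Σp², which is 47% to 62%.

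The working value is 36.7% (correlation 0.7, split 20/55/25), rounded to 37% below.

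**4. What 20 points overall requires.** Gain needed in discordant women = 20 / d.

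| d | Gain needed in discordant women |
|---|---|
| 62% | 32 points |
| 48% | 42 points |
| 37% | 54 points |
| 20% | 100 points |
| below 20% | impossible |

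If discordant women also have 50% under AFC dosing, the most the AMH arm can reach is 50 + 50d: 68% at d = 37% and 74% at d = 48%. If they have only 35% under AFC, concordant women must be at (50 − 0.37 × 35) / 0.63 = 59%. The target is then reachable at d = 37%, but discordant women must rise from 35% to 35 + 54 = 89%.

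**5. Power of two tests with 100 per arm.** Assumptions: 50% in concordant women and in discordant women under AFC; two-sided 5%; 200,000 simulated trials per setting.

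| d | Discordant women, AFC to AMH | Overall difference | All women | Discordant women only |
|---|---|---|---|---|
| 36.7% | 50% to 80% | 11.0 points | 36% | 78% |
| 16% | 50% to 80% | 4.8 points | 11% | 44% |
| 48% | 50% to 80% | 14.4 points | 55% | 88% |
| 36.7% | 50% to 70% | 7.3 points | 19% | 42% |
| 36.7% | 50% to 60% | 3.7 points | 9% | 14% |

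Type I error was about 5% to 6% for both tests.

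**6. Precision for the same all-women difference.** Take d = 0.367 and 50% to 80% in discordant women.
- As planned: 1.96 × √(0.50 × 0.50/100 + 0.61 × 0.39/100) = 13.7 points.
- Through discordant women, allowing for the estimation of d: variance = 0.367² × (0.50 × 0.50 + 0.80 × 0.20)/36.7 + 0.30² × 0.367 × 0.633/200 = 0.00150 + 0.00010 = 0.0016. The half-width is 1.96 × 0.040 = 7.9 points.

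Simulated intervals gave 13.8 and 8.3 points, so about 14 against about 8. The gain shrinks as d rises: the same formula gives about 10 points at d = 62%, where simulated intervals gave 10.9.

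**The case against.** The strongest reply is that the trial compares two dosing policies in first-cycle patients, and the all-randomised comparison answers that question without bias. If most women would get the same dose, a small difference between the policies is a correct finding. This stands, and it is why the planned test should stay. The reply does not explain where 20 points comes from, or why a more precise estimate of the same policy difference should not be reported.

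A second reply is that d is not in the documents. That is true, and every figure that depends on d is conditional. But the sponsor holds the data that would settle it.

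A third reply is that the extra analysis is no rescue. For 50% to 70% in discordant women its power is 42%, and for 50% to 60% it is 14%. This also stands.

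A reader might infer more than the documents support:
- *That the sample size is wrong, or that 93 discordant women per arm are needed.* Section 8.2 frames the effect as a whole-group one ("Assuming that an increase to 70% of appropriate response in the AMH group will be clinically significant"), and 93 per group is correct for it. Nothing there ties the 20 points to women whose dose differs, so the argument does not by itself call for more recruitment.
- *That the plan assumes every woman's dose could differ.* Neither section 8.1 nor section 8.2 says so. They are silent on agreement between the rules.
- *That most of the sample cannot show a difference, or that the target is out of reach.* With weak correlation d could exceed one half. The 68% and 74% ceilings rest on a 50% AFC rate in discordant women, and the trial's own hypothesis could put that rate lower.
- *That discordant women should be the sole primary population.* That is a debatable trade-off. It narrows the direct claim to part of the sample.

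**Conclusion.** The concern holds as a gap in justification and a missed gain in precision. It is not an error in the test or in the arithmetic. The dilution identity follows from section 6: same doses, same day-7 rule, blinded care, and both markers known before treatment. It assumes a true difference of exactly zero in concordant women, which the trial data can check.

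The size depends on d, which the plan does not report. Over the assumed range of 16% to 48%, a 20-point overall difference requires at least 42 points in discordant women, and below 20% it cannot occur. Even with uncorrelated markers (d up to 62% for the splits tried) it requires 32 points. At d of 37% and a 30-point gain in discordant women, the planned test has 36% power and a discordant-women comparison has 78%. That is a favourable effect size; for smaller gains both are weak. The plan should be changed because the needed data already exist and the change uses no extra patients.

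**What to change.** Before the first randomisation:

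1. **Section 8.2.** Cross-tabulate the 214 earlier patients by both dosing rules (3 × 3) and report d with its 95% interval. With n = 214 and d near 37%, the interval is 1.96 × √(0.367 × 0.633/214) = ±6.5 points. Then justify 20 points against d, or restate the detectable effect and power as d times a plausible difference in discordant women.
2. **Section 8.1.** Keep the chi-square test on all randomised women as the policy comparison. Pre-specify as a key analysis AMH versus AFC among women whose two bands, taken from pre-treatment AFC and AMH, differ. Report d times that difference, with an interval that allows for the estimation of d, as the more precise all-women estimate. Show concordant women by arm as a check, with an expected difference of zero. State in advance which analysis carries which claim.

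The cost is one table from data that the centre holds and one more analysis, with no added patients or procedures. The downside is that the added analysis rests on about 73 of 200 women at d of 37% (0.367 × 200), its direct claim concerns only women whose dose differs, and its power for small effects remains low.

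### The primary comparison makes no use of baseline AFC and AMH; a pre-specified adjusted analysis would be a cheap, modest improvement to a valid test

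*Combined protocol and SAP*

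**What the plan says.** The primary outcome in section 7 is "Percentage of subjects having appropriate ovarian response (defined as number of oocytes retrieved being between 6 and 14", both limits included (section 4). Section 8.1 says this percentage "will be compared between the AMH and AFC groups using" a chi-square or Fisher test. It names no covariate, no stratified or sensitivity analysis, and no effect estimate with a confidence interval.

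Both markers are planned for everyone at one visit in the cycle before treatment (section 6). On AFC: "They will undergo transvaginal ultrasound examination to determine the AFC". On the blood sample: it "will also be taken for measurement of reproductive hormones including FSH, LH, E2 and AMH". Neither value can be affected by the dose later assigned.

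The background, before section 3, says that "basal serum AMH level was significantly correlated with AFC, the number of follicles obtained after stimulation and the number of retrieved oocytes". It adds that AMH "has been found useful in prediction of suboptimal and excessive ovarian responses upon ovarian stimulation". It gives no coefficient or R².

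Sections 4 and 6 describe a computer-generated randomisation list and mention no stratification. The section 6 table sets one of three starting doses from the AFC band in one arm and from the AMH band in the other.

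**The concern.** The trial rests on the premise that these markers predict ovarian response, and low and excessive response are the two ways to miss the 6 to 14 target. Leaving both markers out of the analysis has two consequences. Any outcome variation they explain is counted as noise. A chance difference in ovarian reserve between the arms is neither prevented by the randomisation nor corrected in the estimate.

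A second matter is interpretation. A patient whose AFC band and AMH band point to the same row of the dose table gets the same starting dose in either arm. The arms can differ by the starting-dose rule only where the two bands disagree, and the crude comparison cannot show this.

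**Working it through.** **1. The plan's own figure.** Inputs from section 8.2: 50% against 70%, 80% power, type I error 0.05 (taken as two-sided). With the pooled-variance formula and no continuity correction:

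n = [1.96·√(2·0.6·0.4) + 0.8416·√(0.5·0.5 + 0.7·0.3)]² / 0.20² = (1.358 + 0.571)² / 0.04 = 93 per group.

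This matches the stated 93, read as per group. Power is 80.0% at 93 per group and 82.8% at 100. The sample size is right for the unadjusted test.

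**2. Adjustment if strata cost nothing.** Residual variance is multiplied by (1 − R²), so the effective size is n/(1 − R²). R² is assumed. Power at 100 per arm:

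| R² | 0 | 2% | 5% | 10% |
|---|---|---|---|---|
| Power | 82.8% | 83.6% | 84.7% | 86.6% |

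This is optimistic, because splitting 200 patients into strata uses up information.

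**3. Adjustment with that cost included.** Simulated at 100 per arm with nine assumed AFC-band × AMH-band cells and +20 points in every cell. The tests are uncorrected Pearson and Cochran-Mantel-Haenszel (CMH). Cell shares and rates are assumptions.

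| R² of cells | Crude | CMH, nine cells | CMH, about three strata |
|---|---|---|---|
| 0 | 82.9% | 81.2% | 82.2–82.3% |
| 5% | 83.3% | 83.6% | gain of about 0.5 to 1 point on crude |
| 11% | 83.6% | 86.6% | 86–87% |

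At R² = 0, three strata lose 82.9 − 82.3 = 0.6 to 82.9 − 82.2 = 0.7 points, against 82.9 − 81.2 = 1.7 for nine cells. Part of each gap reflects the crude test's slightly higher rejection rate under the null. In a similar set of nine-cell simulations, a continuity-corrected statistic gave only 77–81%.

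**4. What R² might be.** The outcome is a middle band, so a marker that rises with oocyte yield need not have a monotone relation to it. Take an illustrative log-normal model of yield, set to 50% and 70% in band, with an assumed correlation of 0.4 to 0.7 between marker and log yield:
- Yields centred in the band: a linear term explains about 0; linear plus quadratic explains 1 to 13%.
- Yields off-centre, averaged over arms: linear explains about 5 to 17%; with a quadratic term, about 5 to 21%.

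This model does not include dosing by the same markers. A separate mechanistic model of oocyte counts gave 1 to 6% for the nine cells. Bands or curved terms are therefore needed, and the lower part of the range is plausible.

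**5. Chance imbalance.** Under simple randomisation the standardised baseline difference has SD √(2/100) = 0.141, so it exceeds 0.2 in absolute size with probability about 16%. With an outcome SD of about 0.49, the resulting shift is 0.2·√R²·0.49. That is 2.2 points at a linear R² of 5% and 4.4 points at 20%. The standard error is √(0.46/100) = 6.8 points and the target effect is 20.

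**6. Same or different starting dose.** If the effect acts only through the starting-dose rule, an overall 20-point gain must come from patients whose bands disagree. Their share is not in the documents. At an assumed 50% the gain among them must be 20/0.5 = 40 points; at 40%, 20/0.4 = 50; at 30%, 20/0.3 = 67.

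**The case against.** The strongest reply is that nothing here is wrong. A chi-square or Fisher test is valid under randomisation, chance imbalance is already allowed for in its error rate, and the sample size agrees with it. Starting dose is set from these same markers and adjusted on day 7, both of which tend to flatten their link with a 6 to 14 band. At low R² stratifying loses power. All of this stands.

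The uniform-effect assumption is also open to challenge. In simulations that confined the effect to patients whose bands disagree (assumed 32% of patients, +45 points, so 14.4 points overall), nine-cell CMH did worse than the crude test: 50.1% against 55.2% at R² = 0, and 52.3% against 53.8% at 7.7%. This counts against nine cells as the primary test. Three strata were not examined under that pattern, so their gain is shown only for a uniform effect.

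Two stronger readings are tempting. A reader might infer that ignoring reserve inflates the type I error, since the uncorrected chi-square rejects in about 5.5% of simulated null trials and CMH in about 5.0%. The same gap appears at R² = 0, so it comes from the discreteness of the crude statistic and not from imbalance. A reader might also infer that adjustment is free precision, equivalent to a set number of extra patients. The documents give no R², and that conversion ignores the cost of stratifying.

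What the reply does not answer is that the data are already planned, adjustment for baseline values is legitimate, and section 8.1 offers no analysis that uses them.

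**Conclusion.** The concern holds as a modest improvement to a valid plan, and not as a flaw in the test or the sample size. The benefit for power runs from a small loss to about 3 points, assuming 100 per arm, about three strata, a uniform 20-point effect and an R² between 0 and 11%. Protection against imbalance is similarly modest: a shift of roughly 2 to 4 points in the one trial in six where the standardised difference exceeds 0.2, and for an imbalance of about that size. The case for the same-dose against different-dose breakdown does not depend on R². It follows from the dose table itself and would make either a positive or a null result easier to interpret.

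**What to change.** In section 8.1:

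- Pre-specify a baseline-adjusted analysis of the primary outcome that reports the risk difference with a 95% CI. Use one of two forms: Mantel-Haenszel, without continuity correction, over about three reserve strata collapsed in advance from the section 6 AFC and AMH bands; or logistic regression with non-linear AFC and AMH terms and marginal standardisation.
- Define the strata from both markers and identically in both arms, never from the dose received. State how a missing AFC or AMH value is handled.
- Report the crude chi-square beside it, and state in advance which of the two is primary. Keeping the chi-square as primary is acceptable.
- Pre-specify a supportive breakdown by whether a patient's AFC and AMH bands imply the same or different starting doses.

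The cost is a few sentences and a little more analysis work, with no new data, visits or patients and no change to treatment. The downside is a small loss of power if the adjusted analysis is primary and the markers prove not to be prognostic for the 6 to 14 band.

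### Does the drop-out allowance in section 8.2 use a different denominator from the primary outcome, leaving power below the stated 80%?

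*Combined protocol and SAP*

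**What the plan says.** Section 8.2 takes its control rate from the centre's unpublished data, "50% of our patients have appropriate ovarian response when using AFC to determine gonadotrophin dosing as in current practice", and sets the target with "Assuming that an increase to 70% of appropriate response in the AMH group will be clinically significant". It concludes that "we require a minimum of 93 subjects to demonstrate a significant difference between the AMH and AFC groups with 80% power", and then adds the allowance: "To allow for drop-outs, a total of 200 subjects (i.e. 100 per group) will be recruited". No drop-out rate is given; the 7 per arm is simply 100 − 93.

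Section 4 describes the comparison as "The proportion of subjects having appropriate ovarian response, defined as the number of oocytes retrieved being 6 to 14 inclusive", and section 7 lists the primary outcome as "Percentage of subjects having appropriate ovarian response (defined as number of oocytes retrieved being between 6 and 14". Section 4 also says "Participating subjects will be randomized into either (i) AFC or (ii) AMH group". Section 6 sends women to trigger and retrieval, with these exemptions stated: "except for those with zero follicle developing to beyond 10 mm after 12 days of stimulation, or when these are contraindicated for other medical reasons".

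Section 8.1 names the test (chi-square or Fisher's exact) but no analysis set. Nowhere is drop-out defined, and nowhere does the plan say how a started cycle without retrieval is classified.

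**The concern.** Recruiting 100 to end with 93 assumes that drop-outs are removed from the analysis. A percentage of subjects, where subjects are the women randomised, suggests that they stay in and count as not appropriate. On that reading the sample-size step and the outcome use different denominators. Keeping drop-outs as failures shrinks both rates and the gap between them, so the extra 7 women per arm would not fully protect the stated power.

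Two things would be at stake: a modest loss of power, and a denominator left open until results are known. Bias between arms is not at issue. The documents give no frequency of stopped cycles and no reason to expect it to differ by arm, and clinician and patient are both blinded to the assignment.

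**Working it through.** **Inputs (section 8.2).** p₁ = 0.50 (AFC), p₂ = 0.70 (AMH), power 80%, type I error 0.05 (taken as two-sided, which reproduces the plan's figure), 100 recruited per arm, implied allowance 7 per arm.

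**Reproducing the plan's figure.** Pooled two-proportion formula without continuity correction, with p̄ = (p₁ + p₂)/2:

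n = [1.960·√(2p̄(1−p̄)) + 0.842·√(p₁(1−p₁) + p₂(1−p₂))]² / (p₂−p₁)²

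= [1.960·√0.48 + 0.842·√0.46]² / 0.04 = 92.999, so 93 per arm.

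Reading 93 as the total gives only 50.3% power, so the figure is per arm.

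**Power under each reading.** Power = Φ{[(p₂−p₁)√n − 1.960·√(2p̄(1−p̄))] / √(p₁(1−p₁) + p₂(1−p₂))}.

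| Reading | Rates | n per arm | Power (formula) | Power (exact, uncorrected chi-square) |
|---|---|---|---|---|
| 7 per arm not analysed | 50% v 70% | 93 | 80.0% | 79.9% |
| All kept; 50% and 70% already count such women as failures | 50% v 70% | 100 | 82.8% | 83.2% |
| All kept; 50% and 70% exclude such women | 46.5% v 65.1% | 100 | 75.8% | 77.1% |

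In the third row the rates are 0.50 × 0.93 and 0.70 × 0.93, and the difference falls from 20 to 18.6 points. The formula gives Φ[(1.860 − 1.377)/0.690] = Φ(0.701) = 75.8%.

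**Sensitivity of the third row to the number kept as failures, 100 per arm.** 2 per arm: 80.9%. 3: 79.9%. 5: 77.9%. 7: 75.8%. Holding 80% power at 7% kept as failures would take 111 per arm.

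**What the word subjects covers.** The third row needs it to mean everyone randomised. The protocol uses it in at least four ways:
- Section 6: women attending the clinic and being interviewed, before consent and randomisation.
- Section 4: those randomised.
- Section 6: women in stimulation, who are scanned on day 7 and then go to trigger and retrieval.
- Section 8.2: all 200 recruited and, in the same paragraph, the 93 needed after drop-outs.

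The word cannot settle the denominator. The clearest guide is the allowance itself, which in its ordinary sense means that drop-outs are not analysed. That is the first row.

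**Which women are affected.** A zero-follicle cycle yields no oocytes and so falls outside 6 to 14 without any further rule. The control rate is described as a rate among the centre's patients, which reads more naturally as including such cycles than as a rate per retrieval. If so, multiplying by 0.93 on their account counts them twice.

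**The case for a change.** The strongest case for acting is that the silence is real. Nothing in sections 7, 8.1 or 8.2 names the analysis set, the plan foresees women without a retrieval, and an unstated rule could be chosen once results are known. A few sentences would settle it. Moreover, if the 50% and 70% are rates per retrieval, removing never-starters does not by itself secure 80%. With 93 starters per arm and an assumed 2%, 5% or 7% stopped before retrieval and counted as failures, power is 78.0%, 74.8% or 72.7%.

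The silence stands, and so does the arithmetic. The inference that the plan contradicts itself does not. The 75.8% needs three conditions together: the whole allowance used, every such woman counted as a failure, and assumed rates that exclude them. The documents establish none of the three. The per-retrieval figures rest on an assumed stopping rate and on a definition of the 50% that the wording does not favour.

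The natural written rule would analyse women who start stimulation, count a started cycle without retrieval as not appropriate, and leave out those who never start. With 7 per arm never starting, and 50% and 70% as rates per woman starting, it gives 93 per arm and 80.0% power. Writing it down would confirm what section 8.2 already implies and move no number.

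**Conclusion.** No change follows. The stated 80% at 93 per arm is correct on the ordinary reading of a drop-out allowance. Depending on how women without an oocyte count are treated and what the 50% covers, power with the full allowance used runs from 75.8% (77.1% exact) to 82.8% across the three readings tabulated. The adverse case is 4.2 points below the target by the plan's formula (80.0 − 75.8), or 2.8 points by exact calculation (79.9 − 77.1). The favourable case is 2.8 points above it (82.8 − 80.0).

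These figures rest on 7 women lost per arm, which is the recruitment margin and not a documented rate, and on equal losses in the two arms. Since the plan defines neither drop-out nor the denominator of the 50%, the existence of a shortfall cannot be shown, let alone its size. What is left is missing detail: an analyst can count started cycles in their assigned arm, treat a cycle without retrieval as not appropriate, and report never-starters by arm, without departing from anything in the protocol.
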